We will use The Patient Feedback Questionnaire (PFQ). The questionnaire was used in a previous study which evaluates the efficacy of an iCBT program for panic attacks and it was developed by a team of researchers (Ciuca et al., 2011). The questionnaire contains 14 items which evaluate the patients' satisfaction with the platform and several other aspects (quality and utility of different components of the platform). Other items refer to giving improvement suggestions, what they like most, if they would use it again or recommend it to a friend with symptoms related to traumatic experiences. The questionnaire will be administered at post-treatment evaluation.

Drop-out reasons

In order to evaluate the reasons for drop-out we will use a questionnaire developed by Ciuca et al. The questionnaire contains 18 items and each item is considered to be a possible reason (e.g. lack of motivation, lack of time, different expectations, exacerbation of symptoms, interface is too complicated, the treatment pace is too slow or too fast, finding another treatment, getting better, important life events etc.) (Ciuca et al., 2011).

Side effects

We will evaluate negative side effects after completion of the intervention to identify any negative effects of PAXPTSD program. For this at the end of the program, participants will complete the Positive and Negative Effects of Psychotherapy Scale (PANEPS) (Moritz et al., 2018). PANEPS was evaluated in a population of individuals with depression who had completed at least one course of face-to-face psychotherapy. Factor analysis yielded four dimensions: positive effects, side effects, malpractice, and unethical conduct. Internal consistency of PANEPS range between 0.72 - 0.92 (Herzong, Lauff, Rief & Brakemeier, 2019).

Randomization

Participants who return the informed consent and meet all the required criteria are randomly allocated to one of the two conditions . The randomization process is done by a software that was developed to implement a minimization algorithm (Pocock & Simon, 1975) that assures a balanced randomization between groups with respect to certain predefined prognostic (stratification) factors. In this study, two stratification factors have been considered:

SEVERITY(4 levels according to PDS-5 screening scores; level 1: 11 to 23 points; level 2: 24 to 42 points; level 3:

43 to 59 point; level 4: 60-80) and CHRONICITY (2 levels; more or less than 3 months since the traumatic event). The minimization method has been shown to outperform simple randomization in achieving balanced groups (Scott, McPherson, Ramsay, & Campbell, 2002) and its use in clinical trials has been previously recommended as a better option than other randomization methods (Hagino et al., 2004; Scott, McPherson, Ramsay, & Campbell, 2002; Treasure & MacRae, 1998). Before each allocation, the algorithm computes an imbalance score for the two available treatments, taking stratification factors levels into account. The treatment with the lowest imbalance score is then given preference when assigning treatments, but the allocation probability varies for each patient, depending on the actual level of imbalance (Hofmeijer, Anema & van der Tweel, 2008). This method is preferred because it avoids the deterministic allocation of pure minimization (Pond, 2011). The allocation is done by an independent researcher and is concealed, i.e. patients and researchers have no knowledge and no control over the allocation of participants when they randomize a participant with the computer program.

Blinding

Taking into consideration the characteristics of our research it is impossible to keep patients blind to the study procedures and psychotherapists' intervention. All participants are provided with detailed information about the aims and the methodology of the study. They can request more information about the study and they have the right to terminate participation at any time. The personnel in charge of the clinical interviews will be blind to the treatment group allocation. We specifically instruct the participants not to mention group allocation at the post-assessment interview, but also test whether blinding was successful. The clinicians who conduct the diagnostic interviews are required to describe in their report if their participants disclosed their study group, directly or indirectly (Ciuca et al., 2011; Weisel et al., 2018).

Sample size

The effect size for iCBT intervention for PTSD is considered to be small to medium (Kuester, Niemeyer & Knaevelsrud, 2016; Lewis et al., 2019; Sibrandij, Kunovski & Cuijpers). Take this information in consideration we expected an effect size of .60. Based on this effect size, a power of .80 and a level alpha of 0.05 we would need 45 participants in each condition for testing the two tails hypothesis. This recommended sample size has been increased to accommodate an attrition rate of 20%. Thus, the study aims to achieve a total sample of 108.

Statistical analysis

All statistical analyses will be performed using the IBM SPSS Statistics version 20. The aim analysis will be conducted on intention-to-treat samples. We will use a linear mixed effects models approach with full information maximum likelihood estimation. This approach was recommended since it uses all available data and can handle missing data appropriately (Gueorguieva & Krystal, 2004; Meyer et al., 2015; Pond, 2011). The approach emphasizes the assumption that data are randomly missing and does not assume that missing data remain stable as in the last-observation-carried-forward (LOCF) approach (Blankers, Koeter & Schippers, 2010; Meyer et al., 2015). Significance testing of dichotomous data such as diagnostic status will be conducted with chi-square tests. Calculation of within and between- groups effect sizes (Cohen d) will be based on the pooled standard deviations. Regression analyses will be used to identify predictors of treatment outcome. Moderation and mediation analysis will be conducted with multiple regression models, using the PROCESS macro for SPSS (Hayes, 2017), a computational technique that can compute both simple and complex moderation and mediation models. Effect sizes for significant effects will be indicated by Cohen's d.

Consistent with recommendations from CONSORT (Schulz, Altman, Moher, 2011) and SPIRIT (Chan et al., 2013) we mention our intention to perform secondary analyses for minimal treatment users, defined as participants that complete at least 5 of recommended modules and use the intervention program for at least 80 minutes. This definition is based on the specific of our intervention program and the criteria used in other studies (Ciuca et al., 2011; Meyer et al., 2015; Ivarsson et al., 2014).

Discussion

We expect that our program PAXPTSD to be effective for PTSD global severity symptom as well as for subscale for re-experiencing, avoidance, changes in mood and cognitions and hyperarousal. We expect that these results to be maintained (3 months follow-up). These results will be in line with the literature on effectiveness of Internet-delivered cognitive behavior therapy for PTSD showing that Internet-delivered cognitive behavioral interventions are more effective than waitlist control group (Sijbrandij, Kunovski, Cuijpers, 2016). We expect that the effect size for our study to be medium to large and to be in line with other ICBT programs. Internet-based treatments also resulted in moderate to large effects for other disorders such as anxiety (Cuijpers et al., 2009; Reger & Gahm, 2009; Tulbure, 2011) and small to moderate ones for depression (Andersson & Cuijpers, 2009; Cowpertwait & Clarke, 2013; Richards & Richardson, 2012; So et al., 2013). ICBT that provided support resulted in a large effect, whereas a medium effect was obtained without support. Because there are no firm conclusions about the role of the therapist

in ICBT, we decide to keep to minimum the psychotherapist implication. In our study the psychologist will discuss the results of the evaluation in a kickoff meeting as well as offer feedback, respond to question, monitor the progress and offer reminders every week.

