The current study focused on individuals with an established diagnosis of PTSD. The aim of the study is to investigate the effects of guided ICBT on measures of PTSD symptoms, depression, and other anxiety symptoms, as well as quality of life against a control group and the maintenance of the improvements. We expect that the effect size for program PAXPTSD to be in accord with other programs delivered to PTSD patients (Ivarsson et al., 2014; Knaevelsrud et al., 2015; Kuester, Niemeyer & Knaevelsrud, 2016; Spence et al., 2011; Sijbrandij, Kunovski & Cuijpers, 2016).

METHODS/DESIGN

The study is reported in line with the CONSORT 2019 statement (Consolidated Standards of Reporting Trials) and the SPIRIT 2013 Statement (Standard Protocol Items: Recommendations for Interventional Trials).

This study is a two-armed randomized controlled trial (RCT) with one active treatment condition (TC) and a waiting list control group (WL). Individuals from WL will receive the intervention 3 months after the study begins.

1. Guided internet-based cognitive behavioral program for Posttraumatic Stress Disorder (PAXPTSD): Participants will complete the PAXPTSD with guidance from a psychologist. The guidance includes a kickoff meeting discussion of approximately 30 minutes, via Skype, videoconference or telephone after the evaluation, to discuss the results of assessments and to discuss the next steps. After the completion of every module, the psychologists will schedule a session for Q & A with every participant to answer their questions, monitor their progress and offer them feedback. At the end of the program there will be another 30 minutes discussion for debriefing using Skype, videoconference or telephone. All participants will complete the standard program for general symptoms of PTSD and it is composed from 11 modules. Besides these modules, there are 5 facultative modules for specific aspects associated with PTSD (depression, guilt, shame or anger). Facultative modules are activated for every participant by his psychologist according to co-morbidity symptoms.

2. *Waiting list control group*: participants from this group will not receive any kind of intervention for 12 weeks. At the end of the waiting period the participants will receive the intervention program if they want this (after 3 months of study begins) and we will check if they receive any treatment for PTSD and associated problems in this period.

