Clinician interviewing and self-report assessments will take place at screening (T0), pre-treatment assessment (T1), post-assessment 11 weeks after randomization (T3) and 3 months follow-up (T4). There will be also weekly mood assessment. All self-report measures are administered through internet (secure links are used and all the data are

encrypted) and the diagnostic interviews are conducted face to face or via telephone. The questionnaires, which were not yet validated for Romanian population, were previously translated in Romanian and underwent a rigorous back-translation process to ensure a good adaptation. The version we acquired was approved by the author(s) of questionnaires. See **Table 2** for an overview of all assessments. Adherence to assessment completion will be monitored throughout the study. In case of noncompliance participants will be contacted after 7 days (14, 21) to remind them of assessment completion. After 28 days a short message will be sent via text message. The entire communication between psychologist and participants will be inside the platform. In maximum 48 hours after completing the module the psychologist and the participants will schedule the Q and A session for any questions, they will also give feedback and monitor the progress.

Persons who are interested in the program can freely access the study website. The website offers information about PTSD and treatment options and a description of the present clinical trial and information about enrollment.

Participants must offer an online informed consent, and then provide demographic information (age, gender, location and contact information). Then, they have to complete key questionnaires: (1) a screening for the exclusion criteria; (2) one scale to evaluate Posttraumatic Stress Disorder and its severity (PDS-5); and (3) a screening questionnaire for psychiatric comorbidities using Psychiatric Diagnostic Screening Questionnaire (PDSQ).

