Eligible participants are contacted by email to schedule a semi-structured clinical interview face to face or via telephone. The interviews are conducted by two trained clinical psychologists, independent from the study intervention, to verify and confirm the presence of PTSD and the conformity with all the inclusion and exclusion criteria. The eligible participants will receive an email from the administrator of the study with a link where there is a detailed informed consent to the participation in the study. The pre-treatment questionnaires will be completed on the platform by those who are eligible. Participants who offer consent and fulfill all the inclusion criteria are then randomly allocated to one of the two study groups, the treatment condition (TC) or the wait-list control (WL).

Participants in the TC will receive immediate access to the platform and online intervention while the participants in WL will receive login access after 3 months of study intake. After completing the evaluation phase all participants receive a short description and debriefing from psychologists in a kick off meeting of 30 minutes. Participants will receive access to each module after they complete the previous one (one module per week).

[figure not shown]

FIGURE 1 | Study flow

Interventions Development and Content

The PAXonline Standard Program for Post Traumatic Stress Disorder contains 11 modules. Besides these modules, there are 5 facultative modules for specific symptoms associated with PTSD (depression, other secondary emotions such as guilt, shame or anger). The program PAXPTSD contains modules which address important cognitive and behavioral psychotherapy elements which are detailed in **Table 3**. The treatment modules and the manual used to guide the intervention in our RCT were written based on *PAXOnline manual* and on the empirically validated cognitive behavioral models of anxiety disorders (Ciuca, 2019; Clark & Beck, 2011; Leahy, Holland & McGinn, 2011; Resick, Monson & Chard, 2014). The intervention content contains text, audios, short educational video clips, videos and interactive elements like quizzes. Each module can be completed in 15-40 minutes and the participants are provided with a recommended timetable (one or two modules per week, depending if there are necessarily additional modules) (Ciuca, 2019; Miclea, Miclea, Ciuca, Budau, 2010).

Table 3 PAXOnline Posttraumatic Stress Disorder Intervention

Standard program	Short description

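### Waiting-list access opens by elapsed time, not on a completed T3, so a late waiting-list T3 score can be taken after the programme has started

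*Protocol*

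**What the plan says.** **When T3 is due.** Protocol, Procedure, gives "post-assessment 11 weeks after randomization (T3"). Table 2 also puts the post-treatment interview at 11 weeks. METHODS/DESIGN says that the waiting list goes through the assessments much as the treatment arm does.

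**How missed assessments are pursued.** Procedure: "In case of noncompliance participants will be contacted after 7 days (14, 21) to remind them of assessment completion", and then "After 28 days a short message will be sent via text message". The rule is general. It does not name T3, but it covers assessments throughout the study, and no closing date for T3 is given.

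**When the waiting list gets the programme.** There are three statements:
- METHODS/DESIGN, design sentence: "Individuals from WL will receive the intervention 3 months after the study begins".
- METHODS/DESIGN, item 2 (waiting list): "participants from this group will not receive any kind of intervention for 12 weeks", followed by "At the end of the waiting period the participants will receive the intervention program if they want this".
- Procedure, after the allocation sentence: "participants in WL will receive login access after 3 months of study intake".

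All three run on elapsed time, and none names randomisation as its start. The only condition attached is the participant's wish to have the programme.

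**The concern.** T3 is the controlled post-treatment comparison, because the waiting list may start the programme soon afterwards. The comparison needs every waiting-list T3 score to be taken before treatment. The protocol secures this for people who answer on time, but its reminder schedule runs past the day on which the control arm is opened. A waiting-list participant who answers a later reminder may already be working through the modules.

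The exposed measures are the three named under Primary outcomes: PSS-I-5, PDS-5 and PCL-5. If early modules help, such scores narrow the difference between the arms. Late responders are also unlikely to be a random subset of the arm.

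This is a matter of trial conduct. A later analysis plan can exclude a score taken after access, but it cannot recreate an untreated PDS-5 or interview.

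**Working it through.** **Inputs**, all from the protocol: T3 at 11 weeks; contacts at 7, 14, 21 and 28 days (Procedure); waiting period of 12 weeks or 3 months (METHODS/DESIGN, Procedure); one module per week (Procedure).

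**Dates, counted from randomisation**
- T3 due: 11 × 7 = day 77.
- Access: 12 × 7 = day 84, or 3 months taken as 13 × 7 = day 91.
- Margin for a T3 done on time: 84 − 77 = 7 days, or 91 − 77 = 14 days.

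| Contact after T3 due | Day | Days since access (day 84) | Days since access (day 91) |
|---|---|---|---|
| 7 days | 84 | 0 | −7 |
| 14 days | 91 | 7 | 0 |
| 21 days | 98 | 14 | 7 |
| 28 days (text message) | 105 | 21 | 14 |

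With access on day 84, three of the four contacts fall after opening. With access on day 91, two do. At one module per week, someone who answers on day 105 could have done about 21 / 7 = 3 or 14 / 7 = 2 modules. In Table 3 the first three are psychoeducation, breathing training and the first autogenic training module. Desensitisation, cognitive restructuring and the trauma memory come in modules 5 to 7.

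**What dilution could look like (illustration only).** The plan's own sample size reproduces: a two-sample t-test with d = 0.60, two-sided alpha 0.05 and power 0.80 needs 44.6, so 45 per arm, with power 0.804 at 45. Let f be the share of waiting-list T3 scores taken after access and g the share of the full effect already gained. Then d_eff = 0.60 × (1 − f × g). Both f and g are assumptions; the protocol gives neither.

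| f | g | d_eff | Power at 45 per arm |
|---|---|---|---|
| 0.05 | 0.10 | 0.60 × 0.995 = 0.597 | 0.800 |
| 0.10 | 0.25 | 0.60 × 0.975 = 0.585 | 0.784 |
| 0.20 | 0.25 | 0.60 × 0.95 = 0.570 | 0.762 |
| 0.30 | 0.50 | 0.60 × 0.85 = 0.510 | 0.667 |

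The last row asks a lot: half the full effect from two or three introductory modules, in almost a third of the arm. The table shows direction and order of size. It is not an estimate for this trial.

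**The case against.** The planned order is already right: every T3 done on time comes before access, and only late answers are exposed. The reminder text is general and never says that an answer on day 105 is accepted as T3. A person affected must ignore several contacts and yet start the programme promptly. Only introductory modules fit in the overlap, and the bias cannot create a false positive. PCL-5 is completed weekly (Table 2), so an untreated value near week 11 or 12 may exist for that outcome. Figure 1 is not shown and may give the order of T3 and access.

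Most of this stands, and it limits the size of the point. It does not remove it. The text states a calendar rule with no T3 condition, and the general reminders naturally include T3. Weekly PCL-5 does nothing for the PDS-5 or the interview, and it helps only if the late responder kept up the weekly forms.

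A reader might go further in three ways that the protocol does not support:
- *That access could open before T3 is even due, because study intake means consent or screening.* The access sentence directly follows the one on random allocation, so entry at randomisation is the natural reading. No interval between screening and randomisation is given.
- *That the analysis is committed to counting late scores as T3.* The statement "This approach was recommended since it uses all available data and can handle missing data appropriately" describes likelihood estimation in general terms. It sets no visit window, and such rules are commonly left to an analysis plan.
- *That a particular share of the waiting list is affected.* The protocol gives no rate of late answers.

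**Conclusion.** The point holds as a gap in conduct, of modest size. Followed as written, the protocol allows waiting-list T3 scores to be collected up to 21 days (access at 12 weeks) or 14 days (access at 3 months) after the programme opens, if the answer comes on the last listed contact. On-time scores are not affected. The likely bias is small and towards no difference. No figure for lost power can be given.

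This rests on three assumptions: the waiting period counts from randomisation, the general reminder rule applies to T3, and the missing Figure 1 does not make access depend on T3. It is worth correcting because the remedy is cheap and has to be in place before waiting-list logins open.

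**What to change.** 1. State the waiting period once, counted from randomisation.
2. Open a waiting-list participant's login only after that participant's T3 questionnaires and interview are complete, and not before week 12.
3. Set a latest date, for example 3 months from randomisation (about day 91), after which access opens even if T3 is missing, so that nobody is kept waiting indefinitely.
4. Bring the waiting-list T3 reminders forward so that all fall before that date.
5. Flag any waiting-list T3 taken after access, and do not use it as an untreated T3 value in the main analysis.

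Late treatment-arm T3 scores do not have this problem and need not be discarded.

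**Cost.** A wording change, one access rule on a platform that already hosts the self-report assessments, and an earlier reminder schedule. With a 3-month limit, some participants wait up to 91 − 84 = 7 days beyond 12 weeks. A few waiting-list T3 values become missing instead of late. Under Diagnostic interview, a missing post-treatment interview counts as still meeting PTSD criteria, so lost waiting-list interviews would lean the diagnosis comparison towards the treatment arm. That is a reason to schedule the interview early in the T3 period and not to rely on the cut-off date alone.

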The psychologists from the study will be either licensed psychologists or master students at clinical psychology and psychotherapy. They will support the participants' adherence by providing reminders using the messaging application available in the platform or via telephone, offering feedback, and monitoring the progress as well as risk for deterioration. Any crisis or any other adverse events are reported to the research team. In cases when participants forget to complete one session, the psychologists will offer reminders and send messages to participants by using platform messages and telephone messages.

Assessments

Instruments

The selected instruments have already been well established and frequently used in CBT trials for posttraumatic stress disorder in particular, as well as for other anxiety and mood disorders.

Table 2 Measurements and time assessment

Instruments	Abbreviation	Aim	Time of assessment
Clinical administered			
Posttraumatic Stress Disorder Symptom Scale Interview for DSM-5	PSS-I-5	PTSD symptoms	Pre and post treatment assessment (11) weeks
Alcohol Use Disorder Identification Test	AUDIT	Abuse and dependence of alcohol	Screening and exclusion participants with excessive drinking problems
Semi-structured clinical interview for DSM-IV	PDSQ	DSM-IV axis I severity	Pre and post treatment assessment (11) weeks
Self-report ratings			
Primary outcome			
Posttraumatic Diagnostic Scale for DSM-5	PDS-5	Severity of PTSD symptoms	Pre-treatment, middle intervention assessment (after 6 weeks), post-treatment and

			follow-up assessment (3 months)
The Posttraumatic Cognitions Inventory	PTCI	Catastrophic cognitions	Pre-treatment, middle intervention assessment (after 6 weeks), post-treatment and follow-up (3 months)
PTSD Checklist	PCL-5	Screening, monitor	Pre-treatment, every week, middle intervention assessment (after 6 weeks), post-treatment and follow-up (3 months)
Secondary outcome			
Patient health questionnaire-9	PHQ-9	Symptoms and severity of depression	Pre-treatment, every week, middle intervention assessment (after 6 weeks), post-treatment and follow-up (3 months)
General Anxiety Disorder	GAD-7	Symptoms of general anxiety disorder	Pre-treatment, every week, middle intervention assessment (after 6 weeks), post-treatment and follow-up (3 months)
The work and social adjustment scale	WSAS	Functional impairment	Pre-treatment, middle intervention assessment (after 6 weeks), post-treatment and follow-up (3 months)

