Psychiatric diagnostic and screening questionnaire	PDSQ	Axis 1 disorders	Pre-treatment, post-treatment and follow-up (3 months)
Perceived stress scale - 10	PSS-10	Perceived stress levels	Pre-treatment, middle intervention assessment (after 6 weeks), post-treatment and follow-up (3 months)

Additional measures

Credibility/ expectancy questionnaire	CEQ	Expectancy for change and treatment credibility	Administered to 2 and 5 weeks during intervention
A 5-item shortened version of the Medical Outcomes Study Social Support Scale (MOS-SSS)	SS-5	Social support	Pre-treatment, middle intervention assessment (after 6 weeks), post-treatment and follow-up (3 months)
The Patient Feedback Questionnaire	PFQ	Evaluate the patients' satisfaction with the platform, quality and utility of program.	Post-treatment assessment
Positive and Negative Effects of Psychotherapy Scale	PANEPS	Evaluate negative side effects of intervention.	Post-treatment

Diagnostic interview

Comorbidities are assessed using the Romanian adapted version of Psychiatric Diagnostic Screening Questionnaire (PDSQ) (Ciuca, Berger, Crisan, & Miclea, 2016; Ciuca, Berger, Crisan, & Miclea, 2018), which comprises a self-report screening scale, followed by a semi-structured interview delivered by a clinician. The PDSQ scale has good psychometric properties. In the Romanian validation study the mean of the alpha coefficients was .85 and test-retest reliability was above .80 for nine subscales, with a mean test-retest of .85 (Ciuca et al., 2016). Following the screening procedures, all eligible participants are interviewed by one of the psychotherapists. Any mental disorder that reached PDSQ screening cutoff point is assessed during the interview. In order to increase interraters' agreement on assessment protocol, the assessors have to participate in a two days training before study starts. The diagnostic interview is conducted before and after the treatment by clinicians blind to the treatment group. At post-treatment diagnostic interview we are going to count missing data as equivalent to still meeting diagnostic criteria for Posttraumatic Stress Disorder. The procedure is recommended according to intention-to-treat paradigm and was used in several other studies (Hedman et al., 2013; Weisel et al., 2018).

Primary outcomes

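### Negative effects of PAXPTSD are sought mainly through channels that work only in the treated arm, although scheduled PCL-5 and PHQ-9 data would allow a by-arm report of worsening

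*Protocol*

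**What the plan says.** **Aim and instrument.** Under Side effects, the protocol assesses harms after the intervention "to identify any negative effects of PAXPTSD program". The instrument is PANEPS, and Table 2 gives its purpose as "Evaluate negative side effects of intervention" at post-treatment. The scale is about therapy: "Factor analysis yielded four dimensions: positive effects, side effects, malpractice, and unethical conduct".

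**Deterioration and adverse events.** Guidance and Adherence Monitoring lists the guiding psychologists' tasks, including "offering feedback, and monitoring the progress as well as risk for deterioration". The only sentence on adverse events follows in the same paragraph: "Any crisis or any other adverse events are reported to the research team". It names neither a reporter nor an arm.

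**Psychologist contact.** For the guided program, METHODS/DESIGN states: "After the completion of every module, the psychologists will schedule a session for Q & A with every participant". It adds: "At the end of the program there will be another 30 minutes discussion for debriefing". The waiting list receives no intervention for 12 weeks. Under Procedure, the kickoff meeting is for all participants.

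**Other sources.** The drop-out questionnaire offers "exacerbation of symptoms" as one possible reason, with no arm limit. PCL-5 and PHQ-9 are described as weekly, again with no arm limit, and Table 2 also places them at pre-treatment and post-treatment. METHODS/DESIGN says that the waiting list goes through assessments similar to those of the treated arm.

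**The concern.** The program includes writing about the trauma, desensitization and exposure (Table 3, Modules 5, 7, 8 and 9). Some participants may get worse because of it, and others because PTSD fluctuates. A rate seen only in the treated arm cannot tell these apart.

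Take an assumed 10% who worsen under treatment. If 5% worsened on the waiting list, that is an excess of 5 points. If 15% did, it is a reduction of 5 points. The treated-arm figure is the same in both cases.

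Ascertainment adds a second problem. People who talk to a psychologist after each module have more occasions to report an event than people who are waiting. A by-arm count of psychologist-reported events could therefore show an excess under treatment even if the true rates were equal.

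What is at stake is harms reporting, not the efficacy conclusion.

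**Working it through.** The protocol gives no figure for harms, so there is none to reproduce. The check is whether each source gives a rate in both arms, how unequal the contact is, and how precise a by-arm comparison would be.

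**1. Sources compared**

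| Source | Treated arm | Waiting list up to T3 |
|---|---|---|
| PANEPS | end of program | no therapy to rate |
| Psychologists' watch for deterioration | throughout guidance | no counterpart named |
| Adverse-event sentence | in the guidance paragraph | not excluded, but no question or reporter stated |
| Drop-out questionnaire | leavers only | leavers only |
| Check at end of waiting | not applicable | asks only about other treatment received |
| PCL-5 and PHQ-9 at T1 and T3 | scheduled | scheduled (similar assessments) |

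Only the last row gives an outcome for both whole arms. T3 is 11 weeks after randomization (Procedure) and waiting-list access comes after 3 months, so the waiting list is still untreated at T3.

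**2. Scheduled psychologist contacts after the kickoff, at full completion**

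- Lower count: 11 modules (program text) + 1 debrief = 12.
- Upper count: 12 modules (as listed in Table 3) + 5 facultative modules + 1 debrief = 18.
- Waiting list: 0.

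**3. Precision of a by-arm comparison at T3**

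Inputs: total sample 108 (Sample size), so 54 per arm if equal. With the protocol's 20% attrition, 54 × 0.8 = 43.2, taken as 43. The protocol gives no worsening rates, so p = 5%, 10% and 15% are assumed, equal in both arms.

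Half-width of the 95% interval for the difference = 1.96 × √(2p(1−p)/n).

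Example: p = 0.05, n = 54 gives 1.96 × √(0.095/54) = 1.96 × 0.0419 = 0.082.

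| Assumed p | n = 54 per arm | n = 43 per arm |
|---|---|---|
| 5% | ±8.2 points | ±9.2 points |
| 10% | ±11.3 points | ±12.7 points |
| 15% | ±13.5 points | ±15.1 points |

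Power to detect 5% against 10% is 0.16 with 54 per arm and 0.14 with 43. The comparison can only be descriptive.

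**The case against.** The strongest reply is that the trial already holds controlled data. Blinded interviewers rate PSS-I-5 before and after treatment, the self-report scales are taken at T1 and T3, and intention-to-treat mixed models are planned. This stands, and it rules out a stronger reading. A reader might infer that this trial cannot separate negative effects of the program from the course of PTSD. The documents do not support that: the comparison is possible but is not named. The mixed models do not fill the gap, because they compare average course, and a favourable mean can hide a minority who worsen.

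A reader might also infer that PANEPS is misused, or that waiting-list adverse events are excluded. Neither follows. Treated-only use is right for a scale about therapy, and dimensions such as malpractice need no waiting-list rate. The adverse-event sentence has no arm limit, and participants may contact the team at any time.

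It can also be said that deterioration thresholds and harm tables belong in a statistical analysis plan, which is not shown. This is right for the threshold and the table layout. It does not cover the adverse-event question, since a later plan cannot supply answers that were never collected.

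Finally, the comparison could not settle a 5-point difference. That is true. An imprecise controlled estimate is still more informative about attribution than an uncontrolled rate.

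**Conclusion.** The point holds in a limited form. Followed as written, the protocol's named routes to negative effects give no waiting-list rate and unequal ascertainment (12 to 18 scheduled contacts against none), while controlled data that could serve are left without a harm outcome. It is worth correcting because the remedy is cheap, and it leaves the efficacy result untouched.

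The conclusion rests on three readings: that the psychologists' watch belongs to the guided program, as its placement suggests; that waiting-list participants complete T1 and T3, as the protocol says and the efficacy comparison requires; and that the arms are equal in size. The precision of ±8 to ±15 points rests on assumed rates.

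Two matters lie outside the point. Weekly waiting-list collection is implied rather than explicit, since those participants get login access only after 3 months and self-report runs through the platform. The protocol also states no response if suicidal ideation, an exclusion criterion, appears on a weekly PHQ-9. That is a separate clarification, and a reader should not infer from it that no safety procedure exists, since consent pages and the study-flow figure are not available here.

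**What to change.** 1. Add one adverse-event question to the existing T3 self-report form, identical in both arms and worded without reference to therapy. Report PANEPS for the treated arm only, and do not compare psychologist-reported events between arms.
2. Report by randomised arm, as a descriptive harm outcome, the share with deterioration from T1 to T3 on PCL-5 and, separately, on PHQ-9. Fix the threshold for each scale in advance (the analysis plan can hold it), and give the number lacking T3 in each arm. Use T1 and T3 rather than weekly scores.

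The cost is some protocol wording, one form item and one table; both scales are already scheduled. The drawback is the imprecision shown above, so the table should carry intervals and no claim of a difference or of safety.
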